1.1 Synopsis

A) STUDY IDENTIFICATION	
SPONSOR – PROTOCOL CODE NUMBER:	
VERSION (NUMBER & DATE):	
STUDY TITLE: MYPeBS - INTERNATIONAL RANDOMIZED STUDY COMPARING PERSONALIZED, RISK-STRATIFIED TO STANDARD BREAST CANCER SCREENING IN WOMEN AGED 40-70	
ABBREVIATED TITLE: MYPeBS – MY P ersonalized B reast S creening	
INTERNATIONAL COORDINATING INVESTIGATOR: DR [name] FRENCH COORDINATING INVESTIGATOR: DR [name] ITALIAN COORDINATING INVESTIGATOR: DR [name] BRITISH COORDINATING INVESTIGATOR: PROF [name] BELGIAN COORDINATING INVESTIGATOR: DR [name] ISRAELI COORDINATING INVESTIGATOR: DR [name]	
NUMBER OF CENTERS: 852	NUMBER OF RANDOMIZED WOMEN REQUIRED: 85 000 IN EUROPE WITH THE FOLLOWING INCLUSIONS BY COUNTRIES: - 20 000 IN FRANCE - 10 000 IN BELGIUM - 30 000 IN ITALY - 15 000 IN ISRAEL - 10 000 IN UNITED KINGDOM

B) SPONSOR IDENTIFICATION	
NAME:	UNICANCER [name] (France)
CONTACT PERSON:	MRS [name] Project Manager R&D UNICANCER [contact] [contact] email: [contact]

C) STUDY GENERAL INFORMATION
INDICATION: Breast cancer screening in women from the general population aged between 40 and 70 years.

STUDY DESCRIPTION/DESIGN:

MyPeBS is a European randomized, open-label, multicentric, study assessing the effectiveness of a risk-based breast cancer screening strategy (using clinical risk scores and polymorphisms) compared to standard screening (according to the current national guidelines in each participating country), in detecting stage 2 or higher breast cancers.

Women, will be differentially screened for 4 years and then, after an end-of-study mammogram, they will return to the routine screening practice. The main study endpoint will be measured at the end of the four years of intervention.

Furthermore, follow up data will be collected for 15 years from study entry for evaluation of long-term cumulative breast cancer incidence and breast cancer-specific survival (refer to the scheme p 24 and 58).

SUBJECTS

Women from the general population aged 40-70 years old, without personal history of breast cancer or of a high-risk breast cancer condition.

PRIMARY OBJECTIVE:

The study primary objective is to show non-inferiority of the risk-stratified screening strategy in terms of incidence rate of breast cancer of stage 2 and higher (2+) (also referred to as stage 2+ throughout the protocol), compared to standard screening.

SECONDARY OBJECTIVES:

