Further assumptions are a non-inferiority margin of a 25% relative increase in the risk-based arm (null hypothesis $H_0: \lambda_e/\lambda_c \geq 1.25$ with t and c standing for experimental and standard arm, respectively; it corresponds to an absolute increase in the cumulative hazard rate of stage 2 cancer or higher after 4 years up to 120/100000 stage 2 cancers the risk-based arm under H_0), 80% power, 2.5% significance level, 1-sided test. If we assume that under the alternative hypothesis a 10% relative improvement can be expected by the experimental risk-based-stratified screening arm (i.e. $\lambda_e/\lambda_c = 0.9$) due to our anticipated increase in the average numbers of mammograms in the experimental arm, a total of 298 stage 2 breast cancers are required for the non-inferiority assessment using a logrank test. We assume a total of 85,000 participants, 42,500 in each arm, to be included over 2.5 years.

For the primary and key secondary endpoint analysis, each subject will be followed for four years, to be able to compare cycles of mammograms between the 2 screening arms. Later updates of the trial analyses will be performed using longer follow-up.

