8.3 Study populations to be analysed

8.3.1 Definition of per-protocol population for the primary endpoint analysis

The per-protocol (PP) population will include all randomized and eligible women in the arm they were randomized to who complied with their screening recommendation.

Per-protocol definition of compliance (the study entry mammogram, if any, will not be considered) will be used for the primary analysis of the trial and is described below, according to randomization arm:

Per-protocol definition for standard arm:

Standard arm				
(either no mammogram or mammogram(s)/1-2-3 years according to age and country – will be defined individually at entry)				
Population	40-49 (France, Belgium, UK and Israel) 40-44 (All women of Italy) 45-49 (for some women depending the region of Italy)	50-70 (UK)	50-70 (France, Belgium, Italy and Israel)	45-49 (Some region of Italy)
Planned images	No mammogram	Mammogram every 3 years	Mammogram every 2 years	Mammogram every year
Per-protocol definition	≤ 1 mammogram over 4 years	≥ 1 mammogram over 4 years AND < 4 mammograms over 4 years (excluding diagnostic mammograms)	≥ 1 mammograms over 4 years AND < 4 mammograms over 4 years (excluding diagnostic mammograms)	≥ 2 mammograms over 4 years

Per-protocol definition for risk-based arm:

Risk-based arm				
	Low risk	Average risk	High risk	Very high risk
Planned images	Mammogram every 4 years +/- US if dense breast	Mammogram every 2 years +/- US if dense breast	Mammogram every year +/- US if dense breast	Mammogram + MRI every year for women < 60
Per-protocol definition (outside of baseline and end of study mammo)	≤ 1 mammograms over the 4 years	≥ 1 mammograms over 4 years AND < 4 mammograms over 4 years (excluding diagnostic mammograms)	≥ 2 mammogram over 4 years	≥ 3 mammograms over 4 years ≥ 3 MRIs over 4 years

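### The per-protocol bounds that define the primary non-inferiority set overlap between screening strategies, and mammograms are not counted the same way in the two arms

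*Protocol*

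**What the plan says.** The trial compares risk-based screening with standard screening "according to the current national guidelines in each participating country" (synopsis). Section 8.2.1 places the primary non-inferiority test in the per-protocol population. ITT and causal-inference analyses are for sensitivity.

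Section 8.3.1 defines compliance by the number of mammograms over 4 years. For high risk the plan is "Mammogram every year +/- US if dense breast" and the requirement is "≥ 2 mammogram over 4 years". Very high risk has the same yearly mammogram but a floor of 3, plus at least 3 MRIs. Both standard 50-70 cells, UK and non-UK, accept at least 1 and fewer than 4.

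Three rules govern what is counted:
- The sentence introducing the tables leaves out the study-entry mammogram in both arms.
- The row label of the risk-based table also leaves out the end-of-study mammogram. The standard-arm row has no such label.
- Diagnostic mammograms are excluded in the standard 50-70 and average-risk cells only.

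Sections 1.1.14 and 3.1.4 plan an exit mammogram only for low-risk women and for standard-arm women with no screening during the study. For everyone else, they treat the last scheduled mammogram as the end-of-study one.

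The sizing in section 8.1 assumes benefit "due to our anticipated increase in the average numbers of mammograms in the experimental arm".

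**The concern.** A per-protocol set is made primary for non-inferiority so that women who did not follow their strategy do not pull the hazard ratio towards 1. That works only if the compliance rule tells the strategies apart. Here the same attendance can count as compliant in both arms, in groups where the arms are meant to differ. The set can therefore carry the dilution it was chosen to remove. Because the count also depends on an unclear exclusion that appears in one arm's table only, two analysts could build different primary sets from the same data.

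**Working it through.** **1. Counts accepted in section 8.3.1**

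| Cell | Planned mammogram | Counts accepted |
|---|---|---|
| Standard, none planned | none | 0-1 |
| Standard 50-70, UK | every 3 years | 1-3 |
| Standard 50-70, other countries | every 2 years | 1-3 |
| Standard 45-49, some Italian regions | yearly | 2 or more |
| Low risk | exit only | 0-1 |
| Average risk | every 2 years | 1-3 |
| High risk | yearly | 2 or more |
| Very high risk | yearly | 3 or more |

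Counts of 2 and 3 satisfy both the two-yearly and the high-risk rule. A count of 1 satisfies both the low-risk and the standard 50-70 rule.

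**2. A high-risk woman who in fact attends every two years.** Using the scheduling table in section 5.2.5 and leaving out any entry mammogram:
- Last mammogram counted: 2 at every previous-mammogram timing, so compliant. Full yearly attendance gives 4.
- Last mammogram attended not counted: 1 at every timing, so not compliant. Full yearly attendance gives 3.
- Only the last yearly slot not counted: 2 if her previous mammogram was 1 to 2 years before entry, otherwise 1.

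So her status depends on the reading.

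**3. Overlaps that survive the strictest reading**
- An average-risk woman with 3 counted mammograms plus the last one has had 4 in 4 years. That is yearly screening, yet she is compliant with two-yearly.
- A low-risk woman aged 50 or over with one mid-study mammogram plus the exit one has had 2 in 4 years, the control's two-yearly pattern.
- A UK control with 3 is compliant, although a three-yearly interval fits at most 2 into 4 years.

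**4. Who is affected** (age and risk tables, sections 1.1.15 and 1.2.2.1)
- High risk, 50 or over: 0.45×0.40 + 0.30×0.55 = 34.5% of the risk-based arm; 141 + 129 = 270 of 530 expected cancers (51%).
- Low risk, 50 or over: 0.45×0.28 + 0.30×0.15 = 17.1% of the arm; 34 + 12 = 46 expected cancers of all stages.

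**5. The plan's event number.** Inputs from section 8.1: "a non-inferiority margin of a 25% relative increase in the risk-based arm", "a 10% relative improvement can be expected by the experimental risk-based-stratified screening arm" and "80% power, 2.5% significance level, 1-sided test". Ratio to the margin: 0.90/1.25 = 0.72. Freedman: (1.960 + 0.842)² × (1.72/0.28)² = 296.2, or 298 as an even total. Schoenfeld gives 291. The stated 298 is reproduced.

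**6. Power if intensification is lost in high-risk women.** Section 1.2.2.1 expects 50 stage 2+ cancers avoided among the 329 cancers in intensified women. Section 1.2.3 expects at worst 5 extra in de-escalated women. Assumptions: the 50 are spread in proportion, so 50×270/329 = 41 fall in high-risk women aged 50 or over; the net 45 is scaled to a ratio of 0.90; a share f of those women are screened two-yearly but stay in the set. The documents do not give f.

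Ratio = 1 − 0.1×(45 − 41f)/45. Power = Φ(ln(1.25/ratio)×√298/2 − 1.96).

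| f | Ratio | Power |
|---|---|---|
| 0 | 0.900 | 81% |
| 10% | 0.909 | 78% |
| 25% | 0.923 | 75% |
| 50% | 0.946 | 67% |

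Without the scaling, the protocol's own counts give 1 − 45/204 = 0.78 at f = 0 (power 98%) and 0.83 at f = 25% (94%). The 204 is derived in step 7.

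**7. False non-inferiority.** Expected control events: 42,500 × 4 × 120/100,000 = 204. A true ratio of 1.25 needs 0.25×204 = 51 extra stage 2+ cancers. Losing the whole low-risk contrast, at the protocol's 5 cases, moves the ratio by 5/204 = 0.025.

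**The case against.** Four points on the other side have force.

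- **The high-risk example.** A reader might infer that a high-risk woman on the control's two-yearly schedule simply counts as compliant. The documents do not settle this. If the risk-arm exclusion is read together with sections 1.1.14 and 3.1.4, she has one countable mammogram and is left out. What stands is the ambiguity.
- **Direction.** A reader might infer that the overlap makes non-inferiority materially too easy to claim. Lost yearly screening in high-risk women moves the ratio from 0.90 towards 1, which works against the claim. Inflation needs lost contrast in de-escalated women. The 51 extra stage 2+ cases behind a ratio of 1.25 exceed even the 46 all-stage cancers expected among low-risk women aged 50 or over.
- **The standard cell with no planned mammogram.** Its tolerance of 1 may look lax. These women have a mandatory exit mammogram and the standard-arm row does not exclude it, so the tolerance is needed.
- **Raising the high-risk floor to 3 as the primary rule.** This looks like the natural remedy. But a woman diagnosed at her first or second yearly screen might never reach 3, so events could be lost selectively from the risk-based arm. If the last mammogram is not counted, 3 would also demand perfect attendance.

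The ITT and causal-inference analyses in section 8.2.1 mitigate the problem but do not correct the primary set. A supporting set could be specified in the SAP, which is not shown. The bounds and the counting rule, however, are fixed in the protocol.

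**Conclusion.** The concern holds in a limited form. The bounds defining the primary set overlap between strategies, the end-of-study exclusion appears in one arm's table only, and section 8.3.1 has to be reconciled with 1.1.14 and 3.1.4 before the set is well defined. The main effect is on power, about 81% to about 75% if a quarter of high-risk women aged 50 or over are diluted. This rests on an assumed share, on proportional spread of the avoided cancers, and on scaling to 0.90. Any gain in false non-inferiority comes from low-risk women aged 50 or over, and it is small if the protocol's estimate of 5 excess cases is right. This is a worthwhile, inexpensive improvement and does not invalidate the design.

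**What to change.** 1. Reconcile section 8.3.1 with 1.1.14 and 3.1.4, and state for every row which mammograms count. Treat entry, exit and diagnostic mammograms identically in both arms, and adjust for the standard-arm women whose only mammogram is the exit one.
2. Set the analysis upper bound for the UK three-yearly cell at 2.
3. Otherwise keep the present table as primary. Pre-specify a strict per-protocol set, whose bounds do not accept another strategy's schedule, as a required supporting non-inferiority analysis. Judge compliance there against the screens due before diagnosis or censoring, so that early-detected cancers are not dropped.
4. Report mammograms per woman by arm and risk level in both sets.

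These are analysis-set definitions only; no screening schedule is proposed.

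The cost is wording and one more analysis of data already collected. The strict set will have fewer events and a wider interval. The margin is thin already: expected per-protocol events are 204×0.70 + 183.6×0.90 = 308 (183.6 = 204×0.90), or 293 after 5% drop-out, and the plan says that "a total of 298 stage 2 breast cancers are required for the non-inferiority assessment using a logrank test". As an illustration, if the strict set lost 20% of high-risk women and stage 2+ cancers followed the all-stage split (29 + 141 + 129 = 299 of 530), it would lose about 183.6×0.90×0.95×(299/530)×0.20 ≈ 18 events. That is a reason to make the strict set supporting rather than primary.

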5.5 Change of ongoing schedule

Women in the following conditions will remain on study unless they do not wish to, but their schedule might be altered/modified:

- Women who are diagnosed a benign lesion and had to undergo a mammographic control
 - o The participant's schedule may be reorganised to fit with the new schedule of mammograms. Risk must be reassessed with this new information
- Women who are diagnosed with an atypical breast lesion or in situ carcinoma of the breast.
 - o The participant's schedule may as well be reorganised to fit with the new schedule of mammograms. Risk must be reassessed with this new information
- Women who are diagnosed an invasive breast adenocarcinoma or another breast cancer during the trial
 - o They can remain on trial but their risk will be reclassified as high risk and their further schedule adapted accordingly
- Women who had their risk recalculated based on other personal or familial events which have changed their risk level
 - o A new schedule will be provided upon risk recalculation
- Pregnant women
 - o A new schedule will be provided based on participant's availability
- Women who require a modification in their schedule for the advent of a medical condition that is no longer compatible with the scheduled examinations
 - o Women will remain on trial and their schedule adapted accordingly
- Women who require a modification in their schedule for other personal reasons
 - o This must absolutely be limited but may be punctually acceptable

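### Per-protocol membership is a 4-year mammogram count with no stop at diagnosis, so events can be dropped because of when they occurred, unequally by arm and in a direction the protocol does not fix

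*Protocol*

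**What the plan says.** Section 8.3.1 introduces its tables with: "Per-protocol definition of compliance (the study entry mammogram, if any, will not be considered) will be used for the primary analysis of the trial". The cells that matter are:

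- Standard arm, no planned mammogram (mainly ages 40-49): at most 1.
- Standard arm, 50-70, biennial or UK triennial: 1 to 3, diagnostic mammograms excluded.
- Standard arm, 45-49 in some Italian regions (yearly): at least 2.
- Risk-based arm, low risk: at most 1.
- Risk-based arm, average risk: 1 to 3, diagnostic mammograms excluded.
- Risk-based arm, high risk: "≥ 2 mammogram over 4 years".
- Risk-based arm, very high risk: at least 3 mammograms and at least 3 MRIs.

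Only the 1-to-3 cells exclude diagnostic mammograms. Section 8.5 counts events from the day of randomization to 4 years. Section 8.1 leaves non-compliant women out over the 4-year period. Section 5.5 says of women diagnosed during the trial: "They can remain on trial but their risk will be reclassified as high risk and their further schedule adapted accordingly". Section 8.2.1 makes the per-protocol analysis primary for non-inferiority, with the intention-to-treat and causal-inference analyses as sensitivity analyses.

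**The concern.** A woman's cancer ends or changes her screening, so a count taken over 4 years regardless of diagnosis makes membership of the primary set depend on the outcome. Adherent event-free women stay in with all their person-time. Adherent women with an event may not, and the thresholds they face differ between the arms.

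The text leaves open whether diagnostic and post-diagnosis mammograms count in the cells without the exclusion clause, and each reading loses events:

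- **They do not count.** Early events fail the minimum counts. A cancer found on the entry mammogram has zero counted mammograms and fails every cell with a minimum. Yet section 8.2.1 removes prevalent cases only in a sensitivity analysis, so the primary analysis is evidently meant to contain them.
- **They count.** A diagnosed low-risk woman moved to the high-risk schedule can exceed her limit of 1. So can a standard-arm woman aged 40-49 if she is followed yearly after diagnosis.

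The per-protocol result decides the non-inferiority claim and opens the superiority test, so unequal loss of events shifts the estimate on which both depend.

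**Working it through.** **The plan's own figure.** Section 8.1 gives "80% power, 2.5% significance level, 1-sided test", a "non-inferiority margin of a 25% relative increase in the risk-based arm" and an alternative hazard ratio of 0.9, and states that "a total of 298 stage 2 breast cancers are required for the non-inferiority assessment using a logrank test". With the ratio 0.9/1.25 = 0.72, Schoenfeld's formula gives 4 × (1.960 + 0.842)² / (ln 0.72)² = 291. With the per-protocol allocation 0.9:0.7 it gives 296, and Freedman's formula gives 297. The 298 is sound.

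Expected per-protocol events use 42,500 per arm, 5% drop-out, 10% and 30% non-compliance, and 120 per 100,000 per year (0.0048 over 4 years):

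- Standard: 42,500 × 0.95 × 0.70 × 0.0048 = 135.7.
- Risk-based at hazard ratio 0.9: 42,500 × 0.95 × 0.90 × 0.0048 × 0.9 = 157.0. Total 293.
- Risk-based at the margin: 174.4 × 1.25 = 218.0.

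**Weights from the protocol.** The section 1.2.2.1 table gives 530 expected cancers per arm: high 299, average 144, low 87; ages 50 and over total 246 + 184 = 430. From section 8.1, the share of standard-arm stage 2+ events at 50 and over is 105/122.5 = 0.857. The UK share is 10,000/85,000 = 0.118.

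**Assumptions not in the protocol.** Constant hazard over 4 years, perfect adherence, and the mammogram histories below. An event is lost if the cell rule is not met. If f is the share of events lost, R = (1 − f risk-based)/(1 − f standard) multiplies the true hazard ratio. The one-sided error at a true ratio of 1.25 is Φ(−1.96 − ln R / SE), with SE = √(1/d₁ + 1/d₂) and d₁, d₂ the remaining events in each arm.

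*A. Only mammograms up to diagnosis count; simple version.* The second yearly mammogram falls uniformly in years 1-2, so the high-risk loss is 1.5/4 = 0.375. The first biennial one falls uniformly in years 0-2, so the loss is 1/4 = 0.25.
- Risk-based: (299 × 0.375 + 144 × 0.25)/530 = 0.279.
- Standard: 430 × 0.25/530 = 0.203.
- R = 0.721/0.797 = 0.904; remaining events 157.1 and 108.1; SE = 0.125; error = 0.125.

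*B. As A, with the scheduling rules in sections 1.1.14 and 5.2.5 and last mammogram uniform over the past 2 years.* Half of high-risk women are screened at entry, which is not counted, so their second counted mammogram is at year 2. High-risk loss = (0.375 + 0.50)/2 = 0.4375.
- Risk-based: (299 × 0.4375 + 144 × 0.25)/530 = 0.315.
- Standard, with UK women first screened in years 1-3: 0.857 × (0.882 × 0.25 + 0.118 × 0.50) = 0.240.
- R = 0.90; error about 0.13. Of 293 expected events, about 211 remain.

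*C. As B, half of events screen-detected.* High-risk loss = 0.5 × 0.4375 + 0.5 × 0.1875 = 0.3125, where 0.1875 is the chance of detection at the first counted screen.
- Risk-based: (299 × 0.3125 + 144 × 0.125)/530 = 0.210. Standard: 0.120. R = 0.90; error about 0.15.

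*D. All women screened at or just before entry, none screen-detected.*
- Risk-based: 443 × 0.50/530 = 0.418.
- Standard: 0.857 × (0.882 × 0.50 + 0.118 × 0.75) = 0.454. R = 1.07.

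*E. As A, but a diagnostic mammogram counts in the high-risk cell.* Only events before the first counted mammogram are lost: 0.5/4 = 0.125.
- Risk-based: (299 × 0.125 + 144 × 0.25)/530 = 0.138. Standard: 0.203. R = 1.08.

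*F. Yearly post-diagnosis mammograms count, in both arms.* A diagnosis in the first 2 years gives at least 2 further mammograms, so the at-most-1 cells lose 0.50. Simulated losses are 0.055 (standard 50-70), 0.063 (average risk) and 0 (high risk).
- Risk-based: (87 × 0.50 + 144 × 0.063)/530 = 0.099.
- Standard: 0.857 × 0.055 + 0.143 × 0.50 = 0.119. R = 1.02.

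| Case | Standard lost | Risk-based lost | R | 1.25 appears as | One-sided error |
|---|---|---|---|---|---|
| A | 20% | 28% | 0.90 | 1.13 | 0.125 |
| B | 24% | 31% | 0.90 | 1.13 | 0.13 |
| C | 12% | 21% | 0.90 | 1.12 | 0.15 |
| D | 45% | 42% | 1.07 | 1.33 | 0.008 |
| E | 20% | 14% | 1.08 | 1.35 | 0.005 |
| F | 12% | 10% | 1.02 | 1.28 | 0.016 |

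With other mammogram histories under the up-to-diagnosis reading, entry mammogram not counted, R ran from 0.90 to 0.99 for screen-detected shares of 0.25 to 0.7.

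**The case against.** A reader might infer that the rule removes more events from the risk-based arm and so inflates the error of a false non-inferiority claim. The protocol does not support that as a fixed conclusion. The high-risk cell lacks the diagnostic-mammogram exclusion just as the at-most-1 cells do. It cannot be said that a high-risk woman diagnosed at her first counted screen can never reach 2: a diagnostic or follow-up mammogram may take her there. On those readings (E and F), or with everyone screened around entry (D), the distortion runs the other way.

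The inputs are also approximate. The 530-cancer table covers all stages, so its 56% high-risk share (299/530) may not hold for stage 2+ events. Case A treats UK women as biennial. None of the cases applies the at-least-2 rule to the Italian 45-49 group. All of this stands, and it limits what can be said about direction and size.

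Two further arguments carry less weight. The intention-to-treat and causal-inference analyses would help to expose a distortion, but for non-inferiority they are sensitivity analyses and do not repair the primary set. Counting conventions can be left to a statistical analysis plan, but here the protocol itself states the numeric rule and its 4-year window.

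**Conclusion.** The defect stands: membership of the primary population depends on whether and when the cancer occurs, through thresholds that differ by arm. This follows from sections 8.3.1 and 8.5 without outside assumptions.

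The size and sign rest on assumptions about mammogram history, event timing, the screen-detected share and which mammograms count. Across the cases examined, R runs from about 0.90 to about 1.08. At the lower end a true hazard ratio at the margin appears as about 1.13 and the one-sided error is about 0.13 (0.15 in case C) instead of 0.025. At the upper end the error falls to about 0.005 and the bias works against non-inferiority. A larger loss in the risk-based arm is plausible if only mammograms up to diagnosis count, but case D shows that it is not certain even then. Events are lost in every case, which also costs power.

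**What to change.** Reword section 8.3.1 as follows:

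- Judge compliance against the examinations due under each woman's own schedule up to the earliest of breast cancer diagnosis, death, withdrawal or 4 years.
- Treat a woman with nothing yet due by that date as compliant.
- Exclude diagnostic and post-diagnosis mammograms in every cell of both tables.

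No event is then lost for being early, R from this source is 1.00, and about 293 expected per-protocol events remain against the 298 required. The cost is the rewording and some programming. Sections 7.7 and 11.1.2 already provide for collecting examination dates and results.
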